5.3.2.3. Secondary efficacy analyses

For each of the secondary endpoints, values at each assessment visit over the treatment period and changes from baseline for each PROs questionnaires total score to evaluate the RA activity will be presented (absolute and relative variation). 95% CI will be provided.

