### 5.2 SECONDARY (6-MONTH CORE PERIOD)

- To assess the change of the RAID score from baseline (to W4, W12, and W24) in patients with moderately to severely active RA and inadequate response or intolerance to current csDMARD or TNF inhibitors, treated with sarilumab in combination with csDMARD and/or monotherapy.
- To assess the effect of sarilumab in combination with csDMARD and/or monotherapy on other patient-reported outcomes (global assessment of disease activity, disability, morning stiffness, fatigue, anxiety/ depression, mood disorders, and physical activities), in patients with moderately to severely active RA and inadequate response or intolerance to current csDMARD or TNF inhibitors.
- To assess the efficacy of sarilumab in combination with csDMARD and/or monotherapy using DAS28-ESR and CDAI in patients with moderately to severely active RA and inadequate response or intolerance to current csDMARD or TNF inhibitors.
- To assess the safety of sarilumab in combination with csDMARD and/or monotherapy in patients with moderately to severely active RA and inadequate response or intolerance to current csDMARD or TNF inhibitors.

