(14) **Hospital Anxiety Scale (issue from HADS)**

Total score of anxiety is the sum of tick boxes of columns A (see Appendix D). The range of the total score of anxiety value is 0-21.

(15) **Multidimensional Assessment of Thymic States (MATHys):**

The MATHys is a visual analog scale consisting of 20 items varying from 0 to 10 (see Appendix H). These items corresponded to five dimensions: emotional, cognition, psychomotor function, motivation and sensory perception.

Total score is the sum of the 20 items. The measure is the number of centimetres from the left hand anchor. Items measured from 0 to 10 are: 1; 2; 3; 4; 11; 12; 13; 14; 15; 16; 19; 20 and items measured from 10 to 0 are : 5; 6; 7; 8; 9; 10; 17; 18. A score of 0 corresponds to inhibition of the state evaluated by the item. A score of 5 indicates no change from the patient's usual state and a score of 10 corresponds to excitation for the evaluated state. An overall score of between 0 and 200 is thus obtained. This scale is not devoted to make a diagnosis of mood state but allow to determine the general level of inhibition/activation processes (lower scores indicate general inhibition and higher scores indicate general excitation).

The subscore for **emotional** is obtained by the sum of items: 3; 7; 10; 18. This range is 0 (hyporeactive)-40 (hyperreactive).

The subscore for **cognition** is obtained by the sum of items: 5; 9; 12; 14. This range is 0 (Retardation)-40 (Acceleration).

The subscore for **psychomotor function** is obtained by the sum of items: 2; 11; 19. This range is 0 (Retardation)-30 (Acceleration).

The subscore for **motivation** is obtained by the sum of items: 4; 15; 16; 17. This range is 0 (Decrease)-40 (Increase).

The subscore for **sensory perception** is obtained by the sum of items: 1; 6; 8; 13; 20. This range is 0 (Decrease)-50 (Increase).

See: Chantal Henry, Katia M'Bailara, Flavie Mathieu, Rollon Poinot, Bruno Falissard Construction and validation of a dimensional scale exploring mood disorders: MATHys (Multidimensional Assessment of Thymic States). BMC Psychiatry. 2008; 8: 82.

(16) **Functional Assessment of Chronic Illness Therapy – Fatigue (FACIT-F) per item and total score**

The FACIT measurement system is a comprehensive compilation of questions that measure health related QOL in patients with chronic illnesses. The FACIT-F includes the 13 items.

FACIT-F score is the sum of items, this range is 0 to 52. High FACIT-F scores represent less fatigue.

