APPENDIX B: DECISION TABLES

To evaluate the variation of each total score of the PROs in classes, decision tables below will be used.

Total RAID score		At Vx	
		Acceptable status	Non acceptable status
At baseline	Acceptable status	Unchanged (Acceptable status)	Worsening
	Non acceptable status	Improvement	Unchanged (Non acceptable status)

Figure 3: Decision table for the variation of the total RAID score in classes

HADS scores		At Vx		
		Normal	Borderline Abnormal	Abnormal
At baseline	Normal	Unchanged (Normal)	Worsening	Worsening
	Borderline Abnormal	Improvement	Unchanged (Borderline Abnormal)	Worsening
	Abnormal	Improvement	Improvement	Unchanged (Abnormal)

Figure 4: Decision table for the variation of the HADS scores (anxiety and depression) in classes

HAQ-DI scores		At Vx			
		Without any difficulty	With some difficulty	With much difficulty	Unable to do
At baseline	Without any difficulty	Unchanged (Without any difficulty)	Worsening	Worsening	Worsening
	With some difficulty	Improvement	Unchanged (With some difficulty)	Worsening	Worsening
	With much difficulty	Improvement	Improvement	Unchanged (With much difficulty)	Worsening
	Unable to do	Improvement	Improvement	Improvement	Unchanged (Unable to do)

Figure 5: Decision table for the variation of the HAQ-DI domain scores in classes

IPAQ total score		At Vx		
		Low physical activity	Moderate physical activity	High physical activity
At baseline	Low physical activity	Unchanged (Low physical activity)	Improvement	Improvement
	Moderate physical activity	Worsening	Unchanged (Moderate physical activity)	Improvement
	High physical activity	Worsening	Worsening	Unchanged (High physical activity)

Figure 6: Decision table for the variation of the IPAQ classification in classes

Comparison	Classes
Value at Vx < Value at baseline	Decrease
Value at baseline = Value at Vx	Unchanged
Value at baseline < Value at Vx	Increase

Figure 7: Decision table for the size of the rheumatoid nodule evolution in classes

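### Signed change in MATHyS, a two-ended scale, describes net activation but cannot show return to the patient's usual state, and its percentage change has no clear meaning

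*SAP*

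**What the plan says.** Protocol 5.2 sets a secondary objective on other patient-reported outcomes, naming "morning stiffness, fatigue, anxiety/ depression, mood disorders, and physical activities". Mood disorders are listed apart from anxiety and depression. MATHyS is the planned instrument whose cited validation paper concerns mood disorders.

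SAP Appendix A (15) defines the scale. At the low end, "A score of 0 corresponds to inhibition of the state evaluated by the item". For the middle and the high end, "A score of 5 indicates no change from the patient's usual state and a score of 10 corresponds to excitation for the evaluated state". Twenty items are summed: "An overall score of between 0 and 200 is thus obtained". The same entry gives the reading of the total: "lower scores indicate general inhibition and higher scores indicate general excitation". The questionnaire in Protocol Appendix B likewise tells patients that the middle of each line is their usual state.

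The planned analysis is the general one for questionnaire totals. SAP 5.3.2.3 reports values at each visit and "changes from baseline for each PROs questionnaires total score to evaluate the RA activity will be presented (absolute and relative variation"). Appendix A (6) defines absolute change as visit minus baseline, and relative change as that difference divided by baseline. SAP 3.1 summarises quantitative data by mean, median, SD, interquartile range, range and 95% CI. SAP 5.1.3 lists MATHyS items and five dimension scores as well as the total.

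**The concern.** On RAID or HADS, a fall has one meaning. On MATHyS, a move from 80 to 100 and a move from 120 to 100 both bring the patient back to the usual state, but they enter the mean with opposite signs. No planned summary measures nearness to the centre. The item and dimension scores are two-ended too, so reporting them does not supply one. A near-zero mean change could therefore be read as showing that mood was unaffected when many patients had in fact returned to their usual state.

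The relative change has a separate fault. Dividing by baseline presumes that zero means none of the quantity. Here zero is maximal inhibition, so the same distance travelled gives a larger percentage from the inhibited side than from the excited side.

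**Working it through.** **Inputs from SAP Appendix A (15).** There are 20 items scored 0-10, with the usual state at 5. The dimensions have 4 items (emotion), 4 (cognition), 3 (psychomotor), 4 (motivation) and 5 (sensory perception).

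**Stated range and midpoints.**
- Total: 20 x 10 = 200, which reproduces the SAP's 0-200. Centre: 20 x 5 = 100.
- The five dimensions use each of items 1-20 once, and their maxima sum to 40 + 40 + 30 + 40 + 50 = 200.
- Dimension midpoints: 4 x 5 = 20 (emotion, cognition, motivation), 3 x 5 = 15 (psychomotor), 5 x 5 = 25 (sensory).

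**Cancellation in the signed mean (assumed case).** Let a share p of patients start at 100 - d, the rest at 100 + d, and let all return to 100. Then:
- mean signed change = p x d - (1 - p) x d = d(2p - 1)
- mean change in |total - 100| = -d, whatever p is
- share of movement hidden, for p of at least 0.5 = 1 - (2p - 1) = 2(1 - p)

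With d = 20:

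| Below : above centre at baseline | Mean signed change | Mean change in distance | Share hidden |
|---|---|---|---|
| 50:50 | 0 | -20 | 100% |
| 60:40 | +4 | -20 | 80% |
| 70:30 | +8 | -20 | 60% |
| 80:20 | +12 | -20 | 40% |
| 90:10 | +16 | -20 | 20% |
| 100:0 | +20 | -20 | 0% |

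With the 112 evaluable patients of the protocol summary, the 50:50 row would be reported as 0.0 with a 95% CI of about -3.8 to +3.8.

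**A smoother case (also assumed).** Let baseline totals be normal with SD 25, and let every patient move halfway to 100. The mean signed change is 0.5 x (100 - baseline mean). The mean change in distance is -0.5 times the mean of |baseline - 100|.
- Baseline mean 100: signed 0, distance about -10
- Baseline mean 90: signed +5, distance about -10.8
- Baseline mean 80: signed +10, distance about -13

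The more one-sided the sample, the less the signed mean misses.

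**Relative change.**
- 80 to 100: 20/80 = +25.0%
- 120 to 100: -20/120 = -16.7%
- Even split: (25.0 - 16.7)/2 = +4.2%, although the mean change in points is 0

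**Limit of the distance score.** Ten items at 3 and ten at 7 sum to 30 + 70 = 100. That patient has distance 0 on the total without being at the usual state on any item.

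**The case against.** The best defence is that the plan uses the scale as documented. Appendix A (15) says the scale is not meant to diagnose a mood state and describes it as giving the general level of inhibition or activation. A mean signed change answers that question. This stands, and it is why the signed change should stay.

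Some of the problem would also be visible already. SD, interquartile range and range are planned, so narrowing around 100 could be noticed, though nothing quantifies it. The exploratory cognition model in SAP 5.3.2.5.3 takes the middle tertile as reference, but it concerns baseline profiles, not change. HADS covers anxiety and depression and is unaffected.

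Four stronger readings are tempting and are not supported:
- A reader might infer that a shift past the centre towards excitation would be reported as a gain. Neither document calls a MATHyS rise a gain, and Protocol 11.4.2.3 says all analyses are descriptive. The risk lies in interpretation.
- A reader might infer that Appendix B promises a MATHyS table and omits it, since it says "To evaluate the variation of each total score of the PROs in classes, decision tables below will be used". That concerns scores in classes, and SAP 5.1.3 defines no classes for MATHyS. FACIT-F has no table either.
- A reader might infer that a large minimum share of the effect must be lost. The share can be nil, and the baseline mix is unknown.
- A reader might infer that distance from 100 should replace the signed score. The documents give no validation of such a score. The usual state may itself be an ill state after long disease, and several upper anchors describe more energy or more wish to communicate. Movement above the centre could therefore be welcome.

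Splitting results by baseline side has its own hazard. Assume mean 100, SD 25, a baseline-to-visit correlation of 0.7 and no true change. The lower group would still move by about (1 - 0.7) x 25 x 0.80 = +6 and the upper group by -6. Without a control arm this regression to the mean would look like normalisation. The overall distance summary is less exposed, because the entry criteria do not select on MATHyS.

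**Conclusion.** The point holds in limited form. As planned, the MATHyS summaries describe net activation and cannot show return to the usual state. Between 0% and 100% of such movement would be hidden, depending on how patients divide around 100 at baseline. The illustrations assume complete or halfway return to the centre; the documents supply no distribution to narrow the range.

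The objection to the percentage change needs no assumption about the mix, since it follows from where zero lies on the scale.

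Importance is minor to moderate: MATHyS is one of several descriptive secondary outcomes and no test or decision rests on it. It does, however, serve a part of the objective that is named separately, in a study whose rationale (Protocol 4.2) stresses domains little assessed before.

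**What to change.** In SAP 5.3.2.3 and Appendix A (15):
- Drop the relative variation for MATHyS.
- Keep the signed change as the description of net inhibition or activation.
- Add, as a supplementary summary, the change from baseline in |total - 100| and in each dimension's distance from its midpoint (20 for emotion, cognition and motivation; 15 for psychomotor; 25 for sensory perception), with 95% CI at W4, W12 and W24.
- State that neither direction of the signed change alone means benefit, and word any conclusion on the distance score as departure from the patient's own usual state.
- Treat any display by baseline side as descriptive only, with a regression-to-the-mean caveat.

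Record the change in SAP 1.7 as made after the analysis of baseline data described in SAP 7. If that analysis included the MATHyS total, it can already show how patients divide around 100.

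The cost is SAP text and a few derived variables from data already collected, with one more derived score per visit for the total and each dimension. Two limits remain and should be stated: the distance score does not remove cancellation within a patient (the dimension distances help only in part), and it does not settle whether the usual state is a healthy one.

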5.3.2.4. Safety analyses

All AEs (Serious AE (SAE), AE of special interest (AESI), Treatment-Emergent AE (TEAE), AE leading to death, TEAE leading to death) will be presented by System Organ Class (SOC) sorted by internationally agreed order¹ and Preferred Term (PT). A TEAE is defined as an AE occurring in the time from the first injection of IMP up to 14 days after the last injection. In case of AE/TEAE leading to death, cause of death will be provided.

Laboratory safety variables, vital signs and ECG values will be presented at each assessment.

A frequency table of the number and percentage of subjects will be provided for prior and concomitant therapies by therapeutic class (ATC). The table will be sorted by decreasing frequency of anatomic category followed by all other therapeutic classes. In case of equal frequency regarding anatomic categories, alphabetical order will be used.

The following definitions will be applied to laboratory parameters and vital signs

- The potentially clinically significant abnormality (PCSA) values are defined as abnormal values considered medically important by the Sponsor according to predefined criteria/thresholds based on literature review and defined by the Sponsor for clinical laboratory tests, vital signs (PCSA list provided in [Appendix J](#)).
- PCSA criteria will determine which patients had at least 1 PCSA during the on-treatment period, taking into account all evaluations performed during the on-treatment period, including unscheduled or repeated evaluations. The number of all such patients will be the numerator for the on-treatment PCSA percentage.

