### **7.2.2 Exclusion criteria related to the current knowledge of Sanofi compound**

- E 11. Pregnant or breastfeeding woman
- E 12. Women of childbearing potential not protected by highly-effective contraceptive method(s) of birth control (as defined in the informed consent form and/or in a local protocol addendum/amendment) over the study period and for at least 3 months following the last dose of sarilumab, and/or who are unwilling or unable to be tested for pregnancy
- E 13. History of severe allergic or anaphylactic reactions to human, humanized, or murine monoclonal antibodies (or to any of the excipients associated to sarilumab)
- E 14. Immunization with a live/attenuated vaccine within 4 weeks prior to Baseline
- E 15. Stage III or IV cardiac failure according to the New York Heart Association classification
- E 16. History of previous gastrointestinal perforation or diverticulitis
- E 17. Known active current/ recurrent infections (including but not limited to active tuberculosis [TB] or history of incompletely treated TB and atypical mycobacterial disease, hepatitis B and C, and herpes zoster)  
  
NOTE: in case of latent TB infection the patient may be included if a subsequent appropriate anti TB treatment is initiated since at least 3 weeks
- E 18. Positive hepatitis B surface antigen (HbsAg), and/or positive total hepatitis B core antibody, and/or positive hepatitis C antibody (HCV) at the Screening visit
- E 19. Evidence of serious uncontrolled concomitant disease, including severe uncontrolled hypercholesterolemia or hypertriglyceridemia
- E 20. Patients with any of the following laboratory abnormalities at the Screening or Baseline visit:

- Hemoglobin <8.5 g/dL
- White blood cells <3000/mm^3
- Absolute neutrophil count <2000/mm^3
- Absolute lymphocyte count <500/mm^3
- Platelet count <150 000 cells/mm^3
- Creatinine clearance <30 mL/min
- AST or ALT >1.5 x ULN.
- Bilirubin (total) >ULN, unless Gilbert's disease has been determined by genetic testing and has been documented
- Total fasting cholesterol >3.50 g/L [9.1 mmol/L]) or triglycerides >5.00 g/L [5.6 mmol/L])

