### **11.4.3 Analyses of safety data**

All safety analyses will be performed on the safety population using the following common rules:

The following definitions will be applied to laboratory parameters and vital signs

- The potentially clinically significant abnormality (PCSA) values are defined as abnormal values considered medically important by the Sponsor according to predefined criteria/thresholds based on literature review and defined by the Sponsor for clinical laboratory tests, vital signs. These abnormal values will be detailed in the Statistical Analysis Plan that will be validated before the database freezing.
- PCSA criteria will determine which patients had at least 1 PCSA during the on-treatment period, taking into account all evaluations performed during the on-treatment period, including unscheduled or repeated evaluations. The number of all such patients will be the numerator for the on-treatment PCSA percentage.

Death. The following deaths summaries will be generated:

- Number (%) of patients who died by study period (treatment-emergent AEs, on-study) and reasons for death summarized on the safety population
- All AEs leading to death (death as an outcome on the AE CRF/eCRF page as reported by the Investigator), by primary SOC, HLGT, HLT, and PT, showing number (%) of patients sorted by internationally agreed order of SOC and alphabetic order of HLGT, HLT, and PT
- TEAE leading to death (death as an outcome on the AE CRF/eCRF page as reported by the Investigator) by primary SOC, HLGT, HLT and PT showing number (%) of patients sorted by internationally agreed order of SOC and alphabetic order of HLGT, HLT, and PT.

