- E 12.** Women of childbearing potential not protected by highly-effective contraceptive method(s) of birth control (as defined in the informed consent form and/or in a local protocol addendum/amendment) over the study period and for at least 3 months following the last dose of sarilumab, and/or who are unwilling or unable to be tested for pregnancy
- E 13.** History of severe allergic or anaphylactic reactions to human, humanized, or murine monoclonal antibodies (or to any of the excipients associated to sarilumab)
- E 14.** Immunization with a live/attenuated vaccine within 4 weeks prior to Baseline
- E 15.** Stage III or IV cardiac failure according to the New York Heart Association classification
- E 16.** History of previous gastrointestinal perforation or diverticulitis
- E 17.** Known active current/ recurrent infections (including but not limited to active tuberculosis (TB) or history of incompletely treated TB and atypical mycobacterial disease, hepatitis B and C, and herpes zoster)
- NOTE: in case of latent TB infection the patient may be included if a subsequent appropriate anti TB treatment is initiated since at least 3 weeks
- E 18.** Positive hepatitis B surface antigen (HBsAg), and/or positive total hepatitis B core antibody, and/or positive hepatitis C antibody (HCV) at the Screening visit
- E 19.** Evidence of serious uncontrolled concomitant disease, including severe uncontrolled hypercholesterolemia or hypertriglyceridemia
- E 20.** Patients with any of the following laboratory abnormalities at the Screening or Baseline visit:
- Hemoglobin <8.5 g/dL
 - White blood cells <3000/mm³
 - Absolute neutrophil count <2000/mm³
 - Absolute lymphocyte count <500/mm³
 - Platelet count <150 000 cells/mm³
 - AST or ALT >1.5 x Upper Limit of Normal (ULN)
 - Bilirubin (total) >ULN, unless Gilbert's disease has been determined by genetic testing and has been documented
 - Total fasting cholesterol >3.50 g/L [9.1 mmol/L] or triglycerides >5.00 g/L [5.6 mmol/L]

Selection criteria (LTE period):

All the patients who will complete the 6-month-core period will be allowed to enter the LTE period, if sarilumab is not yet commercially available in France (as monotherapy or in combination with csDMARDs).

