APPENDIX I: GLOBAL ASSESSMENT OF DISEASE ACTIVITY

Patient global assessment of disease activity

[figure not shown]
Considering all the ways that your rheumatoid arthritis affects you, rate how you are doing on the following scale by placing a vertical mark on the line:

Very
0 m

Physician global assessment of disease activity

Place a vertical mark on the line for how you would assess your patient's current activity:

Very
0 m

**APPENDIX J: POTENTIALLY CLINICALLY SIGNIFICANT ABNORMALITIES (PCSA)
CRITERIA**

Parameter	PCSA	Comments
Chemistry Blood		
Creatinine clearance (Cockcroft-Gault equation) (mL/min)	<15 (end stage renal disease) ≥ 15 - < 30 (severe decrease in Glomerular Filtration Rate (GFR))	FDA draft Guidance 2010
	≥ 30 - < 60 (moderate decrease in GFR) ≥ 60 - < 90 (mild decrease in GFR) ≥ 90 (normal GFR)	Pharmacokinetics in patients with impaired renal function-study design, data analysis, and impact on dosing and labeling
Total Bilirubin	> 1.5 ULN > 2 ULN	Must be expressed in ULN, not in μmol/L or mg/L. Concept paper on DILI – FDA draft Guidance Oct 2007. Internal DILI WG Oct 2008. Categories are cumulative. First row is mandatory. Rows following one mentioning zero can be deleted.
AST (SGOT)	By distribution analysis: > 3 ULN > 5 ULN > 10 ULN > 20 ULN	Enzymes activities must be expressed in ULN, not in IU/L. Concept paper on DILI – FDA draft Guidance Oct 2007. Internal DILI WG Oct 2008. Categories are cumulative. First row is mandatory. Rows following one mentioning zero can be deleted.
	Additional analysis: > 1 – 1.5 ULN > 1.5 – 3 ULN > 3 - 5 ULN > 5 – 8 ULN > 8 ULN	
ALT (SGPT)	By distribution analysis: > 3 ULN > 5 ULN > 10 ULN > 20 ULN	Enzymes activities must be expressed in ULN, not in IU/L. Concept paper on DILI – FDA draft Guidance Oct 2007. Internal DILI WG Oct 2008. Categories are cumulative. First row is mandatory. Rows following one mentioning zero can be deleted.
	Additional analysis: > 1 – 1.5 ULN > 1.5 – 3 ULN > 3 - 5 ULN > 5 – 8 ULN > 8 ULN	
ALT (SGPT) and Total Bilirubin	ALT>3 ULN and Total Bilirubin > 2 ULN	Concept paper on DILI – FDA draft Guidance Oct 2007. Internal DILI WG Oct 2008. To be counted within a same treatment phase, whatever the interval between measurement.
Lipid panel		
Total Cholesterol	≥7.74 mmol/L ≥6.2 mmol/L	Threshold for therapeutic intervention.
LDL Cholesterol	≥4.1 mmol/L ≥4.9 mmol/L	Threshold for therapeutic intervention.
	Triglycerides	
Hematology		
Erythrocytes	≥ 6 x10 ¹² /L	

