White blood cells	≥ 16.0 x10 ⁹ /L	

Hemoglobin	≤115 g/L (Male); ≤95 g/L (Female) ≥185 g/L (Male); ≥165 g/L (Female) Decrease from screening visit ≥20 g/L	
Absolute neutrophil count	< 1.0 x10 ⁹ /L	International Consensus meeting on drug-induced blood cytopenias, 1991. FDA criteria.
Absolute eosinophil count	> 0.5 x10 ⁹ /L or > ULN (if ULN ≥ 0.5 x10 ⁹ /L)	Harrison- Principles of internal Medicine 17th Ed., 2008.
Absolute basophil count	> 0.1 x10 ⁹ /L	
Absolute lymphocyte count	< 0.5 x10 ⁹ /L ≥ 0.5 x10 ⁹ /L – LLN > 4.0 x10 ⁹ /L	
Monocytes	> 0.7 x10 ⁹ /L	
Platelets	< 50 x10 ⁹ /L ≥ 50 - 100 x10 ⁹ /L ≥ 700 x10 ⁹ /L	
Vital signs		
Systolic blood pressure	≤ 95 mmHg and decrease from baseline ≥ 20mmHg ≥ 160 mmHg and increase from baseline ≥ 20 mmHg	To be applied for all positions (including missing) except STANDING.
Diastolic blood pressure	≤ 45 mmHg and decrease from baseline ≥ 10 mmHg ≥ 110 mmHg and increase from baseline ≥ 10 mmHg	To be applied for all positions (including missing) except STANDING.
Heart rate	≤ 50 bpm and decrease from baseline ≥ 20 bpm ≥ 120 bpm and increase from baseline ≥ 20 bpm	To be applied for all positions (including missing) except STANDING.
Physical examination		
Weight	≥ 5% increase from baseline ≥ 5% decrease from baseline	FDA Feb 2007.

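### For laboratory PCSA rows whose absolute thresholds overlap the entry limits, abnormalities that persist from before treatment are counted together with new ones

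*SAP*

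**What the plan says.** SAP section 5.3.2.4 sets the counting rule: "PCSA criteria will determine which patients had at least 1 PCSA during the on-treatment period", and then "The number of all such patients will be the numerator for the on-treatment PCSA percentage". Protocol section 11.4.3 has the same rule, "taking into account all evaluations performed during the on-treatment period, including unscheduled or repeated evaluations". Neither text mentions the patient's status at entry, and neither document plans a shift table or a split of laboratory PCSAs by baseline status.

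The thresholds are in SAP Appendix J. For total cholesterol they are "≥7.74 mmol/L ≥6.2 mmol/L"; for low hemoglobin, "≤115 g/L (Male); ≤95 g/L (Female". The blood pressure, heart rate and weight rows require a change from baseline, and hemoglobin has a further row for a fall of at least 20 g/L from screening. The other laboratory rows are absolute.

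Entry is limited by E20 (Protocol 7.2.2, repeated in SAP 1.3), which excludes "Total fasting cholesterol >3.50 g/L [9.1 mmol/L", "Hemoglobin <8.5 g/dL" and "Absolute lymphocyte count <500/mm" among others. The flow chart places the first hematology, chemistry and lipid samples at D-7 to D-1.

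**The concern.** For the overlapping rows, a man who enters with hemoglobin 100 g/L and stays at 100 g/L counts as an on-treatment PCSA, exactly like a man who falls from 140 to 110 g/L. The table cannot tell the two apart.

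The Protocol synopsis names clinically significant laboratory abnormalities as a safety endpoint. The trial has one arm, so no comparator shows the background rate. Protocol 8.8.2 and 10.6 expect lipids to rise on sarilumab, and Protocol 4.1.1 lists anemia as a feature of the disease. Lipids and hemoglobin are therefore where a reader most needs to separate what eligibility let in from what appeared later. The SAP makes this separation elsewhere: adverse events count as treatment-emergent only from the first injection, and vital-sign PCSAs need a change from baseline.

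**Working it through.** The plan states no figure for this point, so there is nothing to reproduce. The check compares ranges and then illustrates the size.

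**1. Overlap of entry range and PCSA range.** Units: 8.5 g/dL = 85 g/L; cholesterol as printed in E20 (3.50 g/L = 9.1 mmol/L).

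| Row in Appendix J | Admitted at entry | PCSA | Overlap |
|---|---|---|---|
| Total cholesterol | up to 9.1 mmol/L | ≥6.2; ≥7.74 | 6.2–9.1; 7.74–9.1 |
| LDL | no limit | ≥4.1; ≥4.9 mmol/L | whole PCSA range |
| Hemoglobin, men | from 85 g/L | ≤115 | 85–115 |
| Hemoglobin, women | from 85 g/L | ≤95 | 85–95 |
| Lymphocytes | from 0.5 x10^9/L | 0.5 to LLN | whole band |
| Creatinine clearance | from 30 mL/min (Protocol E20; absent from the SAP copy) | bands 30–<60, 60–<90 | both bands |
| ALT/AST, additional analysis | up to 1.5 ULN | >1–1.5 ULN | whole band |
| ALT/AST, main | up to 1.5 ULN | >3 ULN | none |
| Neutrophils | from 2.0 x10^9/L | <1.0 | none |
| Low platelets | from 150 x10^9/L | up to 100 | none |

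The triglyceride threshold is not legible in the text available and was left out.

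**2. General size.** Let p be the share of patients positive at entry, s the share of those still positive on treatment, and i the new-onset rate among the rest. All three are assumptions. The SAP rule reports

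reported = p·s + (1 − p)·i.

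With i = 5% and N = 140:
- p = 5%, s = 50%: 0.025 + 0.0475 = 7.3%. Of 10.2 patients counted, 3.5 (34%) are pre-existing.
- p = 30%, s = 100%: 0.30 + 0.035 = 33.5%. Of 46.9 counted, 42 (90%) are pre-existing.

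**3. Cholesterol illustration with no drug effect.** Assumed, not from the documents: mean 4.8 / 5.2 / 5.6 mmol/L, between-patient SD 0.95, within-patient SD 0.4, three on-treatment visits, baseline cut at 9.1 mmol/L. Simulated results:

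| Threshold | Counted on treatment | Of these, positive at baseline |
|---|---|---|
| ≥6.2 mmol/L | 14% / 25% / 40% | 50% / 57% / 64% |
| ≥7.74 mmol/L | 0.5% / 1.4% / 3.5% | 28% / 33% / 38% |

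Check of the middle case at 6.2: the SD of a single measurement is √(0.95² + 0.4²) = 1.031, and (6.2 − 5.2)/1.031 = 0.97, so 16.6% are positive at baseline. Of the 25.3% counted on treatment, 0.253 × 0.565 = 14.3% of all patients were positive at baseline, leaving 25.3 − 14.3 = 11.0% as new. Among the 83.4% negative at baseline, the new-onset rate is 11.0/83.4 = 13.2%. The same rate for the other two means is about 8% and 20%.

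**The case against.** A fair opponent would make five points.

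- A reader might infer that the PCSA rule ignores baseline throughout, or that an entry abnormality is counted as such. Neither is right. Vital signs, weight and one hemoglobin row use an entry value, and only on-treatment evaluations enter the numerator, so an abnormality must persist or recur to be counted. The reported percentage is literally accurate; what it lacks is attribution.
- Of the four laboratory signals named in Protocol 4.1.2, neutropenia, thrombocytopenia and raised transaminases have no overlap on their main criteria. Only lipids do. This stands and narrows the point.
- The creatinine-clearance row is a full classification running up to normal, so its 60–<90 band is a weak abnormality flag. The ALT/AST >1–1.5 ULN band is labelled as an additional analysis. Both are secondary here.
- Laboratory values are presented at each assessment, and SAP 5.1.4 adds below, within and above normal for hematology. These show the distribution before treatment, but not whether an individual's PCSA is new. The objection stands only in part.
- A split does not isolate a drug effect. With no drug effect at all, new onset at 6.2 mmol/L is still about 8–20%, from visit-to-visit variation. Replacing the overall percentage by new onset would also hide worsening in patients already positive. Both stand, and they shape the fix.

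Separately, SAP Appendix A item 19 converts lipids from g/L to mmol/L with 5.5, whereas E20 implies 9.1/3.50 = 2.6 for cholesterol. It also multiplies hemoglobin in g/dL by 0.1 to obtain g/L. The illustration uses the E20 scale. Those factors are a different defect affecting the same rows.

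**Conclusion.** The point holds for absolute-threshold laboratory rows that overlap the entry range: total cholesterol, LDL, hemoglobin and lymphocytes, and secondarily the reduced creatinine-clearance bands and the lowest ALT/AST band. For these rows the planned percentage mixes persisting and new abnormalities, and no planned output separates them by patient. The overlap itself follows from the documents without assumption.

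The size does not. It depends on how many patients enter positive and stay so, which the documents do not give. Under the assumed cholesterol values, the share of counted patients already positive is 50–64% at 6.2 mmol/L and 28–38% at 7.74 mmol/L, where few patients (0.5–3.5%) are counted at all.

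The documents do not support reading this as an error in E20: an entry limit may lie inside a monitoring range. Nor does it touch the primary endpoint or the main neutrophil, low-platelet and ALT/AST criteria. It is a low-cost improvement to secondary safety tables, worth making because the trial has no control arm.

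**What to change.** In SAP section 5.3.2.4:

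1. Keep the overall on-treatment PCSA percentage.
2. For each absolute-threshold laboratory PCSA, add a split by baseline status, with baseline defined as the last value before the first injection. Report n/N with the PCSA on treatment among patients without it at baseline and, separately, among patients with it at baseline. The hemoglobin-decrease row stays as it is.
3. For the graded rows (cholesterol, LDL, creatinine clearance, ALT/AST), give a shift table from baseline category to worst on-treatment category, so that worsening in patients already positive stays visible.
4. State that new-onset percentages still include visit-to-visit variation and are not estimates of a drug effect.

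The D-7 to D-1 samples already provide the baseline. No new data and no change to eligibility are needed. The cost is one extra split in existing tables, with smaller denominators in each part.
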